4.5.7 Treatment Beyond Initial Radiological Assessment of Disease Progression

As previously described in [Section 1.1.2.4](#), accumulating evidence indicates a minority of subjects treated with immunotherapy may derive clinical benefit despite initial evidence of PD.²³ This phenomenon was observed in approximately 10% of subjects in the Phase 1 study of nivolumab and has also been reported for ipilimumab monotherapy.

Subjects receiving treatment in this study will be permitted to continue treatment beyond initial PD (intracranial metastases using modified RECIST 1.1 criteria; extracranial disease by RECIST 1.1) as long as they meet the following criteria:

- Investigator assesses clinical benefit AND
- Subject is tolerating study drug.

If a patient has disease progression of ≤ 3 intracranial lesions, the patient may receive SRT (single episode) as clinically appropriate and then resume study treatment as outlined in [Section 3.4.2.2](#).

Subjects with confirmed progression (confirmation assessment will occur approximately 4 weeks after initially assessed progression) will be assessed radiographically and by clinical judgment as to whether the subject is deriving clinical benefit from treatment and should continue study treatment or discontinue and enter the follow up/survival phase of the study according to the time and events schedule presented in [Section 5](#). If progression is confirmed, then the date of disease progression will be the first date the subject met the criteria for progression.

All decisions to continue treatment beyond initial progression must be discussed with the BMS Medical Monitor and documented in the study records. Subject must provide written informed consent prior to receiving additional nivolumab treatment. All other elements of the main consent

including description of reasonably foreseeable risks or discomforts, or other alternative treatment options will still apply

For subjects who continue study therapy beyond progression, further progression is defined as an additional 10% increase in tumor burden volume from time of initial PD. This includes an increase in the sum of diameters of all target lesions and/or the diameters of new measurable lesions compared to the time of initial PD. Treatment with study medication should be discontinued permanently upon documentation of further progression.

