8.3 Endpoint Definitions

8.3.1 Tumor Assessment Endpoints

8.3.1.1 Best Overall Response (BOR) per Subject

The best overall response is determined once all the data for the subject is known. It is defined as the best response designation, as determined by the investigator, recorded between the date of first dose of study drug and the date of objectively documented progression or the date of subsequent therapy, whichever occurs first. For subjects without documented progression or subsequent therapy, all available response designations will contribute to the BOR assessment.

In this study, BOR is specified for the intracranial, extracranial, and global compartments based on the (1) modified RECIST 1.1 criteria (intracranial), (2) RECIST 1.1 criteria (extracranial), (3) combination of modified RECIST 1.1 criteria and RECIST 1.1 criteria (global). Image assessment criteria (modified RECIST 1.1 and RECIST 1.1) are presented in [Appendix 3](#).

For the assessment of BOR, all available assessments per subject are considered.

The best overall response for each patient is determined from the sequence of overall (lesion) responses according to the following rules, listed in order of priority:

- CR = At least two determinations of CR at least 4 weeks apart before progression.
- PR = At least two determinations of PR or better at least 4 weeks apart before progression (and not qualifying for a CR).
- SD = At least one SD assessment \geq 6 months after start of treatment.
- PD = At least two determinations of PD at least 4 weeks apart after start of treatment (and not qualifying for CR, PR or SD).

The BOR for each patient will also be determined by the IRRC as specified within the CA209204 Imaging Review Charter.

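### Protocol 8.3.1.1 contradicts itself on best overall response: the definition stops at progression, but the ranked SD rule does not and outranks PD, so a confirmed progressor can be read as clinical benefit

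*Protocol*

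**What the plan says.** **The window.** Protocol 8.3.1.1 opens by defining BOR as the best investigator designation "recorded between the date of first dose of study drug and the date of objectively documented progression or the date of subsequent therapy", whichever is first. Only subjects with neither event contribute all their designations. Protocol 8.4.2 and SAP 4.1 state the same window, and both count tumor-directed radiotherapy and surgery as subsequent therapy.

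**The ranked rules.** Further down, the same section says "For the assessment of BOR, all available assessments per subject are considered". It then ranks four categories, highest first:

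- A complete response needs two such readings, 4 or more weeks apart, both ahead of progression.
- A partial response is next, for subjects without a complete response: "At least two determinations of PR or better at least 4 weeks apart before progression".
- Third is stable disease, and here the wording is "SD = At least one SD assessment" once 6 months have passed since treatment began. Progression is not mentioned.
- Progressive disease is left to the remainder: "At least two determinations of PD at least 4 weeks apart after start of treatment (and not qualifying for CR, PR or SD".

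**The endpoint.** The first paragraph of Protocol 8.4.1 counts SD without a duration. The second paragraph, and SAP 4.1, require SD lasting at least 6 months.

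**The SAP.** SAP 4.1 requires no confirmation of PD. It analyses two sets of BOR: as entered in the CRF without change, and with adjustments. The adjusted set is primary. One adjustment changes SD to PD when SD lasted under 6 months and a radiographic progression date exists that precedes subsequent therapy, or no subsequent therapy is recorded.

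**The concern.** Intracranial clinical benefit rate (CBR) is the primary endpoint, and 8.3.1.1 is where the protocol turns a sequence of scans into the category that decides it. The definition and the ranked rules give different answers for a subject who progresses and later has an SD scan.

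Such sequences are to be expected here. Protocol 4.5.7 allows treatment beyond initial progression, and Protocol 3.1 allows one episode of SRT for intracranial progression, so some subjects will have scans after PD. Protocol 4.5.7 gives later benefit after initial PD as the reason: "This phenomenon was observed in approximately 10% of subjects in the Phase 1 study of nivolumab".

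If a site completes the BOR field from the ranked rules, a progressor can enter the CRF as SD and count as benefit in the unadjusted analysis. A difference between the CRF-based and adjusted CBR would then partly reflect which paragraph of 8.3.1.1 each site followed.

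**Working it through.** **1. Design figures, which are not in dispute.** Inputs from Protocol 8.1 and Table 8.1-1: n = 110, reference rate 40%, alternative 51.8%, two-sided type I error 0.10.

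- The smallest r with P(X ≥ r | n = 110, p = 0.40) ≤ 0.05 is r = 53, with tail probability 0.0499.
- Power is P(X ≥ 53 | n = 110, p = 0.518) = 0.804, which matches the stated 80.4%.
- The Clopper-Pearson 90% lower bound for 53/110 is 40.0%, as tabulated. For 52/110 it is 39.1%.

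**2. One subject under each rule.** Take intracranial PD at Week 6, PD again at Week 12, and SD at Week 30. The 6-weekly scan schedule allows this. By the SAP 8.1.2 conversion, Week 30 is 30 × 7 / 30.4375 = 6.9 months.

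| Rule applied | Week 30 scan used? | Result |
|---|---|---|
| 8.3.1.1 ranked rules, with all assessments | Yes | SD, benefit |
| 8.3.1.1 opening definition, or 8.4.2 | No, window closed at Week 6 | PD, no benefit |
| SAP 4.1 window | No | PD, no benefit |
| SAP adjusted BOR, if the CRF says SD and SD duration stops at progression | Recode applies | PD, no benefit |
| SAP unadjusted CRF BOR, if the CRF says SD | No recode | SD, counted as benefit if taken to last 6 months |

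The last two rows depend on what SD duration means. The visible text gives it no start or end. Counted from first dose to the Week 30 scan it is 6.9 months and the recode does not apply. Stopped at the Week 6 progression it is 6 × 7 / 30.4375 = 1.4 months and the recode does apply.

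**3. The PD rule.** The protocol rule needs two PD determinations at least 4 weeks apart; the SAP needs one. A subject with a single PD scan can therefore be PD under the SAP and not meet the protocol's PD rule.

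**4. The SAP adjustments.** For CR and PR, SAP 4.1 acts on a preceding PD, confirmed or not. It thus provides for CRF responses entered after progression. SD has no matching rule and is caught only through its undefined duration.

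**5. Scale, by assumption.** The documents do not say how many subjects would have SD only after PD. Let the true CBR be 40% and let d percentage points of all subjects be added through such scans. The chance of reaching 53/110 is P(X ≥ 53 | n = 110, p = 0.40 + d):

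| d | Subjects of 110 | Chance |
|---|---|---|
| 0 | 0 | 5.0% |
| 2 points | 2.2 | 11.2% |
| 5 points | 5.5 | 28.2% |

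The base matters. If 2% or 5% is applied only to the 60% without true benefit, p is 0.412 or 0.430 (about 1.3 or 3.3 subjects) and the chance is 8.3% or 15.8%.

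**The case against.** The strongest reply is that the window governs and the ranked rules only sort designations inside it. It is stated in the opening of 8.3.1.1, in 8.4.2, in the synopsis and in SAP 4.1. The endpoint also requires SD of at least 6 months, which one isolated scan after PD does not obviously satisfy. SAP 4.1 makes the adjusted BOR primary and recodes short SD to PD. For SRT cases the window also closes at tumor-directed radiotherapy, and Protocol 8.5.2 and SAP 7.5.1 plan a sensitivity analysis without subjects who had on-study SRT. Much of this stands: on the better reading the example subject is PD, and the adjusted primary analysis should agree.

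Two stronger readings are tempting, and the documents do not support them.

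- A reader might infer that the two-scan PD rule can never be met inside the window, so that post-progression scans must be allowed to set BOR. But 8.3.1.1 determines BOR once all data are known, and Protocol 4.5.7 and 5.4.3 date confirmed progression to the first scan. A later scan can verify PD without being eligible as a best response.
- A reader might take the 10% in Protocol 4.5.7 as an upper bound on misclassification. It describes benefit despite initial PD in a Phase 1 nivolumab study. It is not a rate of confirmed intracranial PD followed by SD past 6 months on this combination, and it bounds nothing here.

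The reply does not remove the contradiction. The rules limit CR and PR to before progression and leave SD without that limit. SD duration is undefined in the visible text, and the CRF-reported BOR is analysed without adjustment. No visible text tells sites which paragraph of 8.3.1.1 to follow. Appendix 3 and the redacted sections cannot be seen and might help.

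**Conclusion.** The point holds as an internal contradiction in the rule for the primary endpoint, together with a conflict between protocol and SAP on how many PD determinations are needed. Read literally, the ranked rules can count a subject with confirmed early intracranial progression as clinical benefit. The documents do not show that such subjects will be counted so in the primary analysis: the adjusted BOR should make them PD, provided that SD duration stops at progression. The exposure is mainly the unadjusted CRF-reported CBR and its agreement with the adjusted one.

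The number affected is unknown. The 11% and 28% above rest on an assumed 2 or 5 points of added benefit at a true rate of 40%, and describe an analysis in which such subjects are left as SD. They show sensitivity and are not a forecast. At the margin one subject matters: 53/110 has a 90% lower bound of 40.0%, and 52/110 has 39.1%. Sample size and stated power are unaffected.

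**What to change.** In Protocol 8.3.1.1:

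- Add to the SD rule that the assessment must come before progression and before subsequent therapy.
- Limit the sentence on available assessments to the BOR window, with later scans used only to verify PD.
- Align the PD rule with SAP 4.1, so that both documents classify PD for this endpoint in the same way.

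In both documents:

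- Measure SD duration from first dose to progression, subsequent therapy or last evaluable scan, whichever applies.
- Report SD seen after progression in a separate descriptive line, outside CBR.

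The cost is wording only, with no new data. The CRF-based CBR may come out slightly lower.

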8.3.1.2 Overall Survival

Overall Survival (OS) is defined as the time from the date of the start of treatment until the date of death. For those subjects who have not died, OS will be censored at the recorded last date of subject contact, and subjects with a missing recorded last date of contact will be censored at the last date the subject was known to be alive.

8.4 Endpoints

8.4.1 Primary Endpoint

Intracranial clinical benefit rate (CBR) defined as the proportion of patients, whose best overall response according to modified RECIST1.1, is either complete response (CR), a partial response (PR) or stable disease (SD).

The primary endpoint is intracranial CBR. It is defined as the proportion of all treated subjects whose best overall response is either a CR or PR or whose best overall response was SD with duration of \geq 6 months, as determined by modified RECIST 1.1 criteria for index intracranial lesions based on investigator review.

8.4.2 Secondary Endpoint(s)

Secondary endpoints are as follows:

- Intracranial ORR and intracranial PFS per modified RECIST 1.1 criteria;
- Extracranial CBR, extracranial ORR, extracranial PFS per RECIST 1.1 criteria

- Global (intracranial + extracranial) CBR, global ORR, and global PFS per a combination of modified RECIST 1.1 criteria for intracranial lesions and RECIST 1.1 for extracranial disease
- OS
- Safety and tolerability will be measured by the incidence of AE adverse events, serious adverse events (SAE), deaths, and laboratory abnormalities.

Overall survival (OS) is defined as the time from first dosing date to the date of death, will be estimated using the Kaplan-Meier product-limit method, with subjects censored at their last known date alive.

Progression-free survival (PFS) is defined as the time between the date of first dose of study drug and the first date of documented confirmed progression, as determined by the investigator, or death due to any cause, whichever occurs first. Subjects who die without a reported progression will be considered to have progressed on the date of their death. Subjects who did not progress or die will be censored on the date of their last evaluable tumor assessment. Subjects who did not have any on study tumor assessments and did not die will be censored on the date of first dose of study drug. Subjects who started anti-cancer therapy without a prior reported progression will be censored on the date of their last evaluable tumor assessment prior to the initiation of subsequent anti-cancer therapy.

Overall response rate (ORR) is defined as the number of subjects who achieve a best overall response of complete response (CR) or partial response (PR) divided by the number of treated subjects. The best overall response is defined as the best response designation recorded between the date of first study dosing date and the date of progression, or the date of subsequent anticancer therapy (including tumor-directed radiotherapy and tumor-directed surgery), whichever occurs first.

Safety and tolerability will be measured by the incidence of adverse events, serious adverse events, deaths, and laboratory abnormalities.

[REDACTED]

[REDACTED]

[REDACTED]

[REDACTED]

[REDACTED]

[REDACTED]

[REDACTED]

[REDACTED]

[REDACTED]

[REDACTED]

[REDACTED]

[REDACTED]

8.5 Analyses

The analyses of primary, secondary, [REDACTED].

8.5.1 Demographics and Baseline Characteristics

Demographic and baseline characteristics will be summarized using descriptive statistics for all treated subjects. Patients will be categorized into 4 groups according to their SRT status (prior to study with or without SRT and on study with or without SRT). Number of enrolled subjects will be summarized. Summarization will be provided for the overall group, by cohort (asymptomatic and symptomatic), and by subgroup (prior to study with or without SRT and on study with or without SRT).

8.5.2 Primary Efficacy Analyses

The primary endpoint of intracranial CBR will be calculated for the overall population and by cohorts (asymptomatic and symptomatic) with its corresponding two sided 90% exact CI using the Clopper-Pearson method. The two-sided 95% CI will also be calculated. A sensitivity analysis using IRRC-assessed intracranial CBR will also be performed.

In addition, a sensitivity analysis will also be conducted to evaluate the impact of SRT on intracranial CBR by excluding the patients who received on-study SRT.

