Asymptomatic subject who are enrolling into Cohort A and become symptomatic during the screening evaluations may be considered for enrollment into Cohort B if they meet all other criteria for Cohort B. No crossover between cohorts is permitted after the start of treatment.

All patients will be treated with the combination regimen of nivolumab 1 mg/kg combined with ipilimumab 3 mg/kg Q3W (4 doses), followed by nivolumab monotherapy (3 mg/kg Q2W) for a maximum of 24 months, or until progression or unacceptable toxicity. The study will close after the last enrolled subject completes 3 years of follow up from the date of first treatment or the study is discontinued by the sponsor.

At any time, if the safety profile of an enrolled subject suggests an unfavorable risk/benefit profile, a decision will be made by the sponsor in conjunction with the investigators whether to pause or continue enrollment. The steering committee will be informed if a safety signal emerges and will be informed of the results of the planned interim analysis.

The use of SRT (single episode) for disease progression of ≤ 3 intracranial lesions is permitted in this study per protocol-defined guidelines. Any subject who receives SRT while on study will be observed for a protocol-defined period before treatment with the study drug(s) can be resumed. The length of the observation period is determined by when in the course of treatment the subject receives SRT - during induction (nivolumab plus ipilimumab) or during maintenance treatment (nivolumab monotherapy). NOTE: To continue on-study after SRT, at least 1 non-irradiated target lesion must remain after SRT treatment.

Any subject who meets criteria for discontinuation following SRT will proceed to follow-up. All subjects who have completed 24 months of treatment with study drugs, or have been discontinued from treatment will continue to be followed for safety, progression, and overall survival for up to 3 years from the date of the subject's first treatment.

SRT = stereotactic radiotherapy

¹ Subjects may continue to receive on study treatment for a maximum of 24 months or until confirmed progression or unacceptable toxicity or patient withdrawal of consent. After discontinuation from treatment with study drug(s) subjects will proceed to follow-up. Subjects who continue to respond at the end of on study treatment may be prescribed study medication through commercial supply or under appropriate care per investigator.

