All patients will be treated with the combination regimen of nivolumab 1 mg/kg combined with ipilimumab 3 mg/kg Q3W (4 doses), followed by nivolumab monotherapy (3 mg/kg Q2W) for a maximum of 24 months, or until disease progression or unacceptable toxicity. The use of SRT (single episode) for disease progression for ≤ 3 intracranial lesions is permitted. (Section 3.4.2.2) Recommended intervals between treatment with study drug and use of SRT, dose delay after SRT, allowable steroid use (≤ 16 mg dexamethasone PO QD), and tapered over no more than 4 weeks), and observation of patients post SRT when treatment is resumed are also specified in Section 3.4.2.2. Any subject who meets criteria for discontinuation following SRT (Section 4.5.5) will proceed to follow-up for safety, progression, and overall survival after discontinuation of study medication based on the assessment schedules presented in Section 5. NOTE: To continue on-study after SRT, at least 1 non-irradiated target lesion must remain after SRT treatment.

A follow-up period of 3 years from the date of first treatment with study drugs is available for all subjects. The study will close after the last enrolled subject completes 3 years of follow up from

the date of first treatment or the study is discontinued by the Sponsor. The study design is presented in [Figure 3.1-1](#):

Figure 3.1-1: CA209204 Study Design

- Subjects may continue to receive treatment for a maximum of 24 months, or until confirmed progression or unacceptable toxicity. After discontinuation from treatment with study drug(s) subjects will proceed to follow-up. Subjects who continue to respond at the end of on study treatment may be prescribed study medication through commercial supply or appropriate care per investigator.
- Use of SRT for progression of ≤ 3 intracranial lesions will be allowed per protocol-specific guidelines (See Section 3.4.2.2). Subjects who require SRT after second episode of disease progression will be discontinued from treatment and proceed to follow-up.
- All subjects who are discontinued from treatment with study drug(s) will proceed to follow-up. See Table 5.1-4 for schedule of follow up assessments.

SRT = stereotactic radiotherapy

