4.5.2.1 SRT and Dose interruptions

If a patient requires SRT for a single episode of intracranial progression in ≤ 3 intracranial metastases, treatment with study drug will be interrupted as specified in [Section 3.4.2.2](#). The protocol specified steroid treatment and taper (≤ 16 mg dexamethasone PO daily tapered in ≤ 4 weeks four week steroid) must be completed before treatment with the study drugs is resumed.

The length of dose delay/dose interruptions for patients receiving SRT is counted from the date of the last dose of study drug. As specified in [Section 4.5.5](#), patients may resume treatment with study drug after the protocol allowed limit of 6 weeks, if approved by the BMS Medical Monitor. Prior to re-initiating treatment in a subject with a dosing interruption lasting > 6 weeks for any reason including on study treatment with SRT, the BMS Medical Monitor must be consulted.

If the patient is unable to resume treatment due to corticosteroid dependence or neurologic symptoms, the patient will discontinue study drug treatment and go to follow-up.

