5.4.3 Confirmation of Scans

Verification of Response: Confirmation of intracranial response will be confirmed by an MRI performed approximately 4 weeks after the initial radiological assessment. If repeat scans confirm overall response (OR), then response should be declared using the date of the initial scan. If repeat scans do not confirm OR, then the subject is considered not to have had an OR.

Verification of Progression: Progression of disease should be verified in cases where progression is equivocal and will be confirmed by an MRI performed approximately 4 weeks after the initial radiological assessment of progression. If repeat scans confirm PD, then progression should be declared using the date of the initial scan. If repeat scans do not confirm PD, then the subject is considered not to have progressive disease.

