7.4.2.5 Dose Omissions

Dose omissions are not permitted for either nivolumab or ipilimumab.

7.4.4 *Diagnostic Procedures*

- By-subject listings of Diagnostic procedures will be provided for all treated subjects.

7.5 *Efficacy*

All summaries will be based on all treated subjects, unless otherwise specified. All summaries will be repeated by cohort and by SRT status, unless otherwise specified.

7.5.1 *Primary Efficacy Analysis*

The primary endpoint of intracranial CBR is determined by modified RECIST 1.1 criteria for index intracranial lesions based on investigator review. The intracranial CBR will be calculated for the all treated population with its corresponding two sided 90% exact CI using the Clopper-Pearson method. The two-sided 95% CI will also be calculated.

CBR based on BOR as reported on CRF will be analyzed using the same methodology as primary endpoint of intracranial CBR based on modified RECIST 1.1.

Central review of all images will be conducted by a Blinded Independent Central Review (BICR) specified in the Imaging Review Charter. In addition to the primary endpoint analysis, a sensitivity analysis using BICR-assessed intracranial CBR will also be performed, where both two-sided 90% exact CI and two-sided 95% CI will be calculated.

In addition, a sensitivity analysis will also be conducted to evaluate the impact of SRT on intracranial CBR by excluding the patients who received on-study SRT. This will be repeated by cohort only.

7.5.2 *Secondary Efficacy Analyses*

Secondary analyses include additional CBR results, Objective Response Rate (ORR), overall survival (OS) including OS within tumor response and prior occurrence of specific AEs, subject follow-up, subsequent therapy and progression free survival.

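### Excluding on-study SRT recipients cannot show the impact of SRT on intracranial CBR, because recipients are selected by intracranial progression

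*Protocol*

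**What the plan says.** **The analysis.** Protocol 8.5.2 plans a sensitivity analysis to "evaluate the impact of SRT on intracranial CBR by excluding the patients who received on-study SRT". SAP 7.5.1 repeats the aim and the method: "by excluding the patients who received on-study SRT. This will be repeated by cohort only".

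**Who gets SRT on study.** Protocol 3.1: "The use of SRT (single episode) for disease progression for ≤ 3 intracranial lesions is permitted". Protocol 4.5.2.1 has the same trigger: "If a patient requires SRT for a single episode of intracranial progression in ≤ 3 intracranial metastases". The synopsis foresees SRT in both induction and maintenance. Subjects can stay on study afterwards: "To continue on-study after SRT, at least 1 non-irradiated target lesion must remain after SRT treatment".

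**The endpoint.** CBR is a proportion of all treated subjects (Protocol 8.4.1, SAP 4.1). Protocol 8.4.2 closes BOR at "the date of progression, or the date of subsequent anticancer therapy (including tumor-directed radiotherapy and tumor-directed surgery), whichever occurs first", and SAP 4.1 has the same cut-off. Protocol 8.3.1.1 differs: it cuts at subsequent therapy without naming radiotherapy, and its PD category needs two determinations. SAP 4.1 requires no confirmation of PD.

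**The splits.** SAP 3 and 7.5 repeat the efficacy summaries by SRT status, which includes on-study SRT yes or no. OS runs from first dose (SAP 4.2). Adverse events are counted from first dose (SAP 6.1.2) and split in the same way (SAP 7.6). Safety with or without on-study SRT is part of a secondary objective (Protocol 1.3.2).

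**The concern.** The stated aim is an effect of SRT, but the method is a change of population. Recipients are identified after baseline by intracranial progression, which itself decides whether a subject has clinical benefit. If BOR is derived as defined, a recipient's BOR is fixed no later than the SRT date, so SRT cannot have altered it. The difference between the analyses with and without recipients therefore carries no information on SRT.

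A reader may nevertheless take a small difference as proof that SRT did not influence the result, or a large one as proof that it did. The question worth asking is whether any assessment made after SRT entered the BOR behind the primary CBR. The exclusion does not answer it.

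The OS and AE splits have a related weakness. A subject must survive to the SRT date to be in the SRT group, and events before SRT are counted in that group.

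**Working it through.** **1. The plan's own figures.** For 53/110 the exact 90% interval is 40.0% to 56.4%, as in Protocol Table 8.1-1. With success at 53 or more of 110, the upper-tail error at 40% is 0.0499 and the power at 51.8% is 80.4%, as stated. These figures are not in dispute.

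**2. Expected shift from the exclusion, with no SRT effect.** Let p be the CBR in all treated subjects, s the share receiving on-study SRT and q the CBR among recipients. The CBR among the rest is (p - s·q)/(1 - s), so

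shift = s·(p - q)/(1 - s).

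Take p = 0.40 (the reference rate in Protocol 8.1). Both s and q are assumptions, since the documents give neither.

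| q | s = 10% | s = 15% | s = 20% |
|---|---|---|---|
| 0 | +4.4 | +7.1 | +10.0 |
| 20% | +2.2 | +3.5 | +5.0 |
| 30% | +1.1 | +1.8 | +2.5 |
| 40% | 0 | 0 | 0 |
| 50% | -1.1 | -1.8 | -2.5 |

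Example: s = 0.10, q = 0 gives 0.10 × 0.40/0.90 = 4.4 points. The sign depends only on whether recipients had less or more prior benefit than the whole group. More is possible: a subject who responds, or is stable for 6 months, and then progresses in maintenance has clinical benefit and may receive SRT.

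**3. The same in counts.** Assume 50/110 with benefit (45.5%, 90% CI 37.4-53.7) and 15 recipients. The last column keeps all treated subjects and counts every recipient as no benefit.

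| Recipients with benefit | After exclusion (90% CI) | Conservative bound (90% CI) |
|---|---|---|
| 2 | 48/95 = 50.5% (41.6-59.4) | 48/110 = 43.6% (35.6-51.9) |
| 5 | 45/95 = 47.4% (38.6-56.3) | 45/110 = 40.9% (33.0-49.2) |
| 8 | 42/95 = 44.2% (35.5-53.2) | 42/110 = 38.2% (30.4-46.4) |

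The lower limit after exclusion falls on either side of 40% although SRT does nothing.

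**4. Could post-SRT scans enter BOR?** By the definition in Protocol 8.4.2 and SAP 4.1, no. In derivation, the primary BOR is the CRF entry with the SAP 4.1 adjustments. Those use a recorded radiographic progression date; none cuts BOR at the SRT date. Protocol 5.4.3 says of equivocal progression: "If repeat scans do not confirm PD, then the subject is considered not to have progressive disease". If no progression date were recorded, a later assessment could remain. Each such benefit would add 1/110 = 0.9 points.

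**5. OS split.** Assume exponential survival with median 12 months, 25% of subjects candidates for SRT at a date uniform over 1.5-9 months, and no SRT effect. The hazard ratio is the added mortality from the SRT date onward, standing for progression.

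| Assumed hazard ratio | Planned split, median OS from first dose (SRT vs none) | Month 6 landmark, median remaining (SRT vs none) |
|---|---|---|
| 1.0 | 17.1 vs 10.6 months | 12.0 vs 12.0 months |
| 1.5 | 13.2 vs 10.6 | 8.0 vs 11.5 |
| 2.0 | about 11.3 vs 10.6 | 6.0 vs 11.1 |

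The planned split mixes immortal time with selection by progression. A landmark removes only the former.

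**6. AE split.** In the same model about 91% of recipients have SRT after day 63, the scheduled day of the fourth combination dose. Most combination-phase events in the SRT group would then precede SRT.

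**The case against.** The best defence is that dropping recipients is a familiar robustness check with no test, pass rule or claim attached, so the complaint is about the word impact. Much of what is needed is also planned: results by on-study SRT status, BOR tabulations and listings (SAP 7.5.2.2), a listing of subsequent therapy including radiotherapy (SAP 7.5.2.7), and a centrally assessed CBR (SAP 7.5.1). It stands that nothing formal rests on the exclusion and that the fix is cheap for this reason. It does not rescue the stated purpose: the visible text names this analysis as the one that evaluates SRT impact, and it cannot do so.

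A reader might infer that post-SRT scans inflated the primary CBR. The documents do not show this. The BOR definition closes at radiotherapy, SAP 4.1 needs no confirmation of PD, the confirmation step in Protocol 5.4.3 is for equivocal progression, and the SAP 4.1 adjustment of CR and PR covers unconfirmed PD with a recorded date. What remains is a missing check.

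A reader might also infer that the exclusion always flatters the result, or that the OS split must favour SRT. Neither follows: the first depends on recipients' prior benefit, the second on how far progression raises mortality.

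On AEs, SAP 7.6.6 plans rates by time interval and SAP 7.6.8 gives time to onset of nervous-system events by SRT status. These add timing, but from first dose and not relative to SRT.

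**Conclusion.** The point holds for the sensitivity analysis. The exclusion conditions on a progression-triggered event and cannot evaluate the impact of SRT on intracranial CBR. With no SRT effect it would shift the estimate by about -2.5 to +10.0 points, assuming a 40% CBR, 10-20% recipients and prior benefit in 0-50% of them. The size is illustrative; the logical defect does not depend on it. The all-treated primary estimate is not shown to be wrong.

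The OS and AE splits are a secondary point. They are descriptive and need a label, plus a before-and-after view for AEs. A Month 6 landmark for OS should not be required: if mortality doubles after progression it shows a larger spurious gap (6.0 vs 11.1 months) than the planned split (about 11.3 vs 10.6).

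Protocol 3.4.2.2, Appendix 3, the Imaging Review Charter, the Data Presentation Plan and some redacted analyses are not visible. A date-based SRT analysis there cannot be ruled out.

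**What to change.** 1. In Protocol 8.5.2 and SAP 7.5.1, make the SRT sensitivity analysis one in all treated subjects, with on-study SRT recipients classified by intracranial BOR from assessments before the SRT date. Add a bound, labelled conservative, that counts every recipient as no clinical benefit. Give 90% and 95% Clopper-Pearson intervals overall and by cohort, with the number of recipients and their pre-SRT BOR.
2. State that the pre-SRT result should equal the primary result if the BOR definition was followed, and that a difference means post-SRT assessments entered the CRF-based BOR.
3. If the exclusion is kept, label it descriptive and not an estimate of SRT impact.
4. Reconcile the BOR rules: Protocol 8.3.1.1 with Protocol 8.4.2 and SAP 4.1, on whether radiotherapy closes BOR and whether PD needs confirmation.
5. Label the on-study SRT splits of OS and AEs as not interpretable as SRT effects. For recipients, report the exposure-adjusted AE rates of SAP 7.6.6 separately for time before and after the SRT date.

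**Cost.** A few sentences and limited reprogramming with methods already in the SAP. The conservative bound needs only counts from planned tables. The sensitivity CBR may be less favourable than the exclusion would have given. Record the change as made after the 09 August 2020 interim database lock.
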